3.5.2. Secondary endpoints

Intervention (surgery, stereotactic radiosurgery, or fractionated radiotherapy) and mortality unrelated to the meningioma.

3.6. Data collection

Data will be collected at each centre by members of the local team. Data will be collected from the patient's medical records and MRI scans. All clinical and radiological information collected for this study by the local investigators should be available routinely and no extra patient assessment will be required. Data will be collected and stored online through a secure University of Liverpool server running the Research Electronic Data Capture (REDCap) web application and using the patient unique study number. Local investigators will be given secure REDCap project server login details. No patient identifiable information will be uploaded or stored on the REDCap database. The study number (site ID_patient ID) is generated by REDCap on creating a new patient record in the database. The clinical team can only view the records of patients from their own centre. All local investigators will store a copy of the link between the patient's unique study number and their patient identifiers on a secure password protected computer, using a blank link file provided by the study team.

3.7. REDCap database

REDCap is a secure web application for building and managing online databases. Access to REDCap will be provided by the Liverpool Clinical Trials Centre (LCTC), University of Liverpool, a partner of the REDCap consortium. Database programmers will oversee the development of a data collection tool (Appendix 1) which can be accessed using any electronic device with

internet access. The database will be built to comply with the UK's Data Protection Act 2018 and the European Union's General Data Protection Regulation (GDPR). Quality assessment of the tool will be done over two phases. Phase 1 will involve local testing of the tool using pre-existing data (11). Phase 2 will expand testing to three to five additional participating centres. After completion of phase 2, the data collection tool will be made live for use by the participating sites.

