To this end, a recent retrospective cohort study of incidental meningioma patients in the United Kingdom (UK) was conducted to assess the utility of combining routinely available radiological and clinical factors to develop a prognostic model for the risk of incidental meningioma progression during active monitoring (11). The model IMPACT (Incidental Meningioma: Prognostic Analysis Using Patient Comorbidity and MRI Tests) could be used as a tool to guide active monitoring strategies for patients with an incidental asymptomatic meningioma within the first 10 years of diagnosis, however validation with external datasets is required.

This international retrospective cohort study of incidental meningioma has the primary aim of externally validating and calibrating the prognostic model IMPACT, accessible using <https://www.impact-meningioma.com>. These data will provide insight into the incidence, epidemiology, presentation, management, and long-term outcomes of incidental meningioma, which will inform the development of clinical guidelines and identify areas for future research.

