3 METHODS

3.1. Study design

This will be a retrospective, international multicentre cohort study. The study will include incidental meningioma patients managed at each participating centre. Cases will be identified by the local site research teams using existing patient medical records. Baseline clinical and radiological characteristics, tumour management, and clinical and radiological outcomes will be collected and recorded (anonymised data) on a secure database by the local investigator. Since this study falls within the remit of clinical outcomes audit, individual patient consent is not required. The study will collect data from the medical records for patients newly-diagnosed over a 2-year period between 1st January 2009 and 31st December 2010. This is an observational study and will not impact on routine patient care.

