3.2. Study population and eligibility criteria

The study will include adults (≥ 16 years of age) with a newly identified incidental intracranial meningioma, as per radiology report, diagnosed between 1st January 2009 and 31st

December 2010. Radiological diagnosis is expected to be based on the presence of an extra-axial lesion with broad-based attachment along the dura showing contrast enhancement. The accepted definition of an incidental finding is “a previously undetected abnormality of potential clinical relevance that is unexpectedly discovered and unrelated to the purpose of the examination”.

Exclusion criteria are as follows:

- History of cranial radiation >5 years from diagnosis
- History of neurofibromatosis type 2
- Surgical resection which revealed a different histopathological diagnosis
- Unavailability of medical notes including scans

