Two competing risk analyses will be performed. One assessing the cumulative incidence rate (CIR) of primary intervention at different time points following diagnosis stratified by PS and ACCI groups and the other will evaluate the CIR of disease progression. The competing event for the former will be non-meningioma-specific mortality either observed during follow-up or after being discharged from outpatient care. Patients who remain under follow-up will be censored at the last outpatient clinic appointment. Patients discharged alive from outpatient care will be censored at the last time they were seen by a healthcare physician up to the date of data entry.

For the disease progression analysis, mortality after hospital discharge could not be used as a competing event as the time interval between discharge and death could have seen radiological changes which meet the disease progression definition. Instead, four events will

be considered competing in nature, discharge from outpatient care, loss to follow-up, death during follow-up or an intervention before disease progression occurred with the first three grouped together. Censoring will only be done for patients who remain under follow-up at the last clinic appointment. To test the equality across CIR groups, the Fine and Gray test will be carried out. Plots of CIRs and 95% confidence intervals (CIs) will also be generated and compared to the training data set (11).

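### The eligibility rules do not exclude patients from the IMPACT training set, so the validation may not be fully external

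*Protocol*

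**What the plan says.** - **Aim.** Protocol section 1 describes IMPACT as a tool "for patients with an incidental asymptomatic meningioma within the first 10 years of diagnosis" and adds "however validation with external datasets is required". Section 2.1 makes external validation the only primary objective.
- **Source of the model.** Section 1 says that "a recent retrospective cohort study of incidental meningioma patients in the United Kingdom (UK) was conducted", citing reference 11. Section 3.10.1 confirms what reference 11 is: the new cumulative incidence curves are to be "compared to the training data set (11").
- **Who enters.** Section 3.1: "The study will include incidental meningioma patients managed at each participating centre". Section 3.2 takes anyone aged 16 or over with an incidental meningioma first diagnosed in 2009 or 2010. It lists four exclusions: earlier cranial radiation, neurofibromatosis type 2, a different diagnosis at surgery, and "Unavailability of medical notes including scans". Section 3.3 has each centre go through all its meningioma patients and drop those who fail these criteria.
- **Who is analysed.** Section 3.10.1 calculates 5- and 10-year IMPACT risks for the whole cohort.
- **Database.** Section 3.7: "Phase 1 will involve local testing of the tool using pre-existing data (11"), followed by "Phase 2 will expand testing to three to five additional participating centres", after which the tool goes live. Section 3.6 keeps patient identifiers out of REDCap, and the link between study number and identity stays with each site.

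**The concern.** A model fitted to a set of patients tends to perform better in those patients than in new ones. If development patients are part of the validation cohort, the validation is not fully external.

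Three planned results would be exposed:

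1. The calibration, Brier score, C-statistic, D-statistic and time-dependent AUC in 3.10.1.
2. The decision to update the model. Section 3.10.2 starts recalibration only if validation shows a poor fit, and optimism from overlap could hide one.
3. The comparison of cumulative incidence with the training set, which would in part compare patients with themselves.

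Overlap would also be hard to notice. Because REDCap holds no identifiers and issues its own study numbers, the central team could not recognise a development patient without help from the site.

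**Working it through.** **Step 1: is there a filter?** Following a hypothetical patient who was in the training set, was diagnosed in 2009-2010 and was managed at a participating centre:

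| Stage | Section | Would the patient be removed? |
|---|---|---|
| Inclusion | 3.1, 3.2 | No |
| Four exclusions | 3.2 | No; none concerns the training set |
| Patient identification | 3.3 | No; it applies the 3.2 criteria |
| Scoring and validation | 3.10.1 | No; all included patients are scored |

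**Step 2: could such patients exist?** Two conditions are needed.

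- *The development centre takes part.* Section 3.7 tests the tool locally on the reference 11 data and then moves to "additional" participating centres. That wording suggests the local site is one of them, but no section says so.
- *Some development patients were diagnosed in 2009-2010.* The model is offered for the first 10 years after diagnosis and was published in 2019, so diagnoses around 2009-2010 are plausible. The protocol gives no diagnosis years, and other recruitment windows would also fit.

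**Step 3: the plan's own sample size.** Inputs from 3.4: 100 events, progression risk 10%, minimum 1500 patients.

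- Patients for 100 events: 100 / 0.10 = 1000, as stated.
- Expected events in 1500: 1500 × 0.10 = 150.

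**Step 4: what would exclusion cost?** Let m be the number of overlapping patients within the 1500. The documents do not give m, so the values below are assumptions. External events = (1500 − m) × risk. The second risk is the lowest that still gives 100 events from 1500: 100 / 1500 = 6.67%.

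| m (assumed) | Share of 1500 | External N | Events at 10% | Events at 6.67% |
|---|---|---|---|---|
| 0 | 0% | 1500 | 150 | 100 |
| 50 | 3.3% | 1450 | 145 | 97 |
| 100 | 6.7% | 1400 | 140 | 93 |
| 200 | 13.3% | 1300 | 130 | 87 |
| 400 | 26.7% | 1100 | 110 | 73 |
| 500 | 33.3% | 1000 | 100 | 67 |

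At 10% risk the 100-event minimum survives the removal of up to 500 patients. At 6.67% there is no slack, and any removal takes the count below 100. This is why the targets should be counted after the exclusion.

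**Step 5: bias in the C-statistic.** It cannot be derived from the documents. As pure assumption, suppose that C in development patients exceeds true external C by 0.05 to 0.10, and treat the pooled value as a weighted average. The inflation is then share × gap: from 0.033 × 0.05 = 0.002 to 0.267 × 0.10 = 0.027. A pooled C is not exactly linear in this way, because pairs across the two groups also count. These figures show an order of magnitude only.

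**The case against.** **Overlap is inferred.** The protocol names no development centre, size or diagnosis window. This stands in full and limits the point to a gap in the rules.

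**The phase 1 sentence is weak evidence of contamination.** Testing a form on known data before go-live is ordinary practice. A reader might infer that the training records stay in the live database, but 3.7 does not say so. The point therefore rests on the exclusion list: even if every test record is deleted, a participating development centre could enter the same patients again under new study numbers.

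**Entry is not compulsory on the text.** A reader might conclude that development patients must be entered. Section 3.1 does not say that all eligible patients are taken (though 3.3 reviews all meningioma patients), and no section confirms that the development centre participates. The text supports only that such patients would be admitted if both conditions in step 2 hold.

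**The protocol treats the two data sets as distinct.** It calls for external data and compares its curves with the training set. That shows intent, but it gives sites no rule to apply. Figure 1, on building the site patient list, could not be seen in the copy available. A filter drawn only there cannot be ruled out, but 3.2 presents its four items as the exclusion criteria.

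**The effect may be small.** With 150 events in 1500 patients, the Hanley-McNeil standard error at an assumed C of 0.70 is about 0.025, similar to the top of the assumed range in step 5. This is fair, but bias and sampling error are different things, and the claim of independence does not depend on the size of the shift.

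**A statistical analysis plan could define the validation set.** It could, but it could act only on patients whom sites had been told to identify, and that instruction belongs with eligibility.

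**Conclusion.** The gap is real and should be closed. As written, sections 3.2, 3.3 and 3.10.1 would admit and score any training-set patient diagnosed in 2009-2010 at a participating centre, in a study whose primary objective is external validation. If there is overlap, performance measures would tend to be optimistic and the poor-fit trigger in 3.10.2 less sensitive.

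The documents establish neither the existence nor the size of any overlap. The conclusion that the validation *is* contaminated, or any particular inflation of the C-statistic or calibration, goes beyond them. The point depends on two unconfirmed conditions: that a development centre takes part, and that some of its development patients fall within the diagnosis window.

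**What to change.** Add a fifth exclusion to 3.2: *included in the IMPACT development cohort (11)*. Have the development centre(s) apply it by checking their local records of that cohort against the study link file, since only they hold the identifiers. State in 3.4 that the 100 events and 1500 patients are counted among non-development patients only.

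The cost is one line of protocol text, one check at the development centre(s), and the loss of any overlapping patients there. At 10% risk that loss is affordable up to 500 patients; at lower risk, other centres would have to make up the number. If no patients overlap, nothing is lost and independence is documented for the TRIPOD report.

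Deleting phase 1 test records before go-live is routine data management, and a sensitivity analysis without the development centre(s) is optional. Neither is needed to resolve the point.

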3.8. Recorded variables

3.8.1. **Baseline clinical variables**

Age at diagnosis, sex, ethnicity, the World Health Organisation (WHO) performance status (PS) and the age adjusted Charlson comorbidity index (ACCI) (Tables 1-2) (17-19). These factors will only be recorded at baseline.

Table 1. WHO performance status classification		Table 2. Age-adjusted Charlson comorbidity index		
Score	Description	Condition		weight
0	able to carry out all normal activity without restriction	Age (years)	<50	0
1	Restricted in strenuous activity but ambulatory and able to carry out light work		50-59	1
2	Ambulatory and capable of all self-care but unable to carry out any work activities; up and about more than 50% of waking hours		60-69	2
3	Symptomatic and in a chair or in bed for greater than 50% of the day but not bedridden		70-79	3
4	Completely disabled; cannot carry out any self-care; totally confined to bed or chair.		≥80	4
5	Dead	Myocardial infarction		1
		Congestive heart failure		1
		Peripheral vascular disease		1
		Hemiplegia		2
		Cerebrovascular disease		1
		Pulmonary disease		1
		Diabetes		1
			With end organ damage	2
		Renal disease		2
		Liver disease	Mild	1
			Severe	3
		Peptic ulcer disease		1
		Cancer		2
			Metastatic	6
		Dementia		1

	Connective tissue disease		1
	AIDS		6
	Hypertension		1
	Skin ulcers/cellulitis		2
	Depression		1
	On Warfarin		1

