3.8.3. Management strategy

Management strategies will include active monitoring and intervention (surgery, stereotactic radiosurgery (SRS), fractionated radiotherapy (fRT) or discharge from outpatient clinic care) (Figure 3). **Active monitoring** is defined as regular surveillance imaging and outpatient clinical observation. Recorded factors will include:

- Number of scans, and interval between them (months)
- For each scan: peritumoural signal intensity, venous sinus involvement and meningioma volume
- Each scan will be examined alongside its corresponding outpatient clinic appointment for any evidence of meningioma-related symptoms (motor/sensory/language/cognitive/seizure/headache/other)
- The outcome of each clinical encounter (i.e. outpatient appointment) will be recorded (resume follow-up/surgery/SRS/fRT/hospital discharge)

Intervention details; if performed, will also be recorded. These will include indication for intervention (clinical-radiological/clinical/radiological/patient preference) and time to intervention. For patients treated with clinical-radiological or clinical progression, status of meningioma-related neurological morbidity will be noted.

For surgery, the following will additionally be recorded:

- Simpson grade (as recorded by the surgeon in the operative notes) (21)
- WHO grade (classified according to the WHO system in use at the time of surgery and updated according to the WHO 2016 classification dependent on pathologists' availability (22)) and presence of any reported brain invasion (yes / no / not reported)
- Postoperative medical and surgical complications recorded at 30 days (Landriel-Ibañez Classification (Table 3) (23))
- Follow-up duration (months)
- WHO performance status pre- and postoperatively and at the last follow-up appointment.
- Recurrence on contrast-enhanced MRI during that time (yes/no) and if recurred then the time to recurrence

For SRS and fRT:

- Fractionated dose (fRT), number of fractions (fRT) and total dose (fRT /SRS)
- Early and late (≥ 3 months) toxicity (assessed by CTCAE v5.0, https://ctep.cancer.gov/protocoldevelopment/electronic_applications/ctc.htm)
- Duration of follow-up post-radiation (months)
- WHO performance status pre- and post-radiation and at the last follow-up appointment
- Progression/regrowth on contrast-enhanced MRI during that time (yes/no) and if progressed/regrew then the time to progression/regrowth

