3.10. Planned statistical analysis

3.10.1. External validation

Using IMPACT, the five- and ten-year estimated risk of disease progression for every patient included in this cohort study will be calculated. Kaplan-Meier method will be used to obtain the observed risks. The predictive performance of IMPACT will be assessed by examining measures of calibration and discrimination. Calibration refers to how closely the predicted 5- and 10-year risk of progression agrees with the observed risk. A calibration plot compares the observed and predicted rates of events for each group. A perfect match indicates accurate calibration. The Brier score for censored survival data will also be calculated, which is a measure of accuracy and is the average squared deviation between predicted and observed risk; a lower score represents greater accuracy. Discrimination is the ability of the risk score to differentiate between those patients who do and those who do not experience disease progression during the study timeframe. This measure is quantified by calculating the C-statistic, D-statistic and Chambless and Diao's time-dependent AUC (area under the receiver operating characteristic curve [ROC]) which are tailored towards censored survival data. Model assumptions will be tested by examination of Schoenfeld residuals, and influential observations will be examined using DFBETA panels.

The effect of patient age, comorbidity, and performance status on the risk of disease progression and intervention will be assessed using a competing risk analysis. Patients will be split based on WHO PS into two categories: 0-1 and 2-4 and stratified by ACCI (Table 1) into three groups: 0-2, 3-5 and ≥ 6 . An ACCI score of ≤ 2 corresponds to patients who are young (<60 years) with few or no comorbidities. An ACCI score of 3–5 corresponds to either an older patient with few comorbidities, or a younger patient with several comorbidities, and an ACCI score ≥ 6 denotes older patient with comorbidities (24).

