9 APPENDICES

9.1. Appendix. 1. Guide for REDCap database developers

Characteristic	Options	Notes
BASELINE CLINICAL CHARACTERISTICS (PAGE/SECTION 1)		
Age (years)	Free field	Required entry
Sex	Dropdown list/check box 
 • Male • Female 	
Ethnicity	Dropdown list/check box 
 • White • Mixed / Multiple ethnic groups • Asian / Asian British • Black / African / Caribbean / Black British • Other ethnic group • NA 	Required entry. Allow one option only. Other ethic group prompts a free text box
Comorbidities	Check box 
 • Hypertension - systolic > 140 or diastolic > 90 and patients on medical treatment • Previous myocardial infarction • Congestive heart failure • Peripheral vascular disease • Previous stroke/TIA - If hemiplegia present, do not check • Hemi/paraplegia • Diabetes which requires medical treatment 	Required entry. Allow multiple options. Note to data collector: Age and comorbidities will be used to calculate the age adjusted Charlson comorbidity index. Each of these is defined in the guide provided

	
 • Diabetes with end-organ damage - if so, do not check diabetes that requires treatment • COPD/Asthma • Renal disease • Mild liver disease - Hep B/C or cirrhosis without portal hypertension • Moderate to severe liver disease - cirrhosis with portal hypertension, jaundice, ascites • Peptic ulcer disease • Cancer - excluding basal cell carcinoma • Metastatic cancer - if so, do not check cancer • Rheumatic or connective tissue disease • HIV/AIDS • Skin ulcers/cellulitis • Depression • Dementia • On Warfarin 	
WHO Performance status	Dropdown list/check box 
 • 0 • 1 • 2 • 3 • 4 	Required entry. Allow one option only
Indication for scan	Dropdown list/check box 
 • Headache • Cerebrovascular accident • Head injury • Audiovestibular symptoms 	Required entry. Allow multiple options. Note to data collector: The meningioma must not be thought to be the cause of these symptoms. Other indications might include lethargy, research, sinusitis, anosmia...etc. Other prompts a free text box

	
 • Visual symptoms • Psychiatric symptoms • Cognitive symptoms • Loss of consciousness • Other 	
NUMBER OF MENINGIOMAS ON 1ST DIAGNOSTIC SCAN (PAGE/SECTION 2)		
Initial scan date	DD/MM/YYYY	Required entry. YYYY can't be ≤2007 or ≥2011

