Outcome	Dropdown list/check box 
 • Resume follow-up (active monitoring) • Surgery • SRS • fRT • Discharge • Lost to follow-up • Dead 	Required entry. Allow one option only Note to data collector: You will be directed to the relevant page/section dependent on the choice. If the patient died or was lost to follow-up after this interval scan, please choose one of the last two options, albeit the intention might have been to continue monitoring or intervene. If the option you choose is set to take place in the future, choose the option, save the data entered and exit the form with no further information required.
SURGERY (SECTION/PAGE 6)		
Surgery date	DD/MM/YYYY	Required entry
Indication for intervention	Dropdown list/checkbox 
 • Clinical-radiological • Clinical • Radiological • Patient preference 	Required entry. Allow one option only
Preoperative WHO PS	Dropdown list/checkbox 
 • 0 • 1 	Required entry. Allow one option only

	
 • 2 • 3 • 4 	
Preoperative comorbidities	
Check box
 
 • Hypertension - systolic > 140 or diastolic > 90 and patients on medical treatment • Previous myocardial infarction • Congestive heart failure • Peripheral vascular disease • Previous stroke/TIA - If hemiplegia present, do not check • Hemi/paraplegia • Diabetes which requires medical treatment • Diabetes with end-organ damage - if so, do not check diabetes that requires treatment • COPD/Asthma • Renal disease • Mild liver disease - Hep B/C or cirrhosis without portal hypertension • Moderate to severe liver disease - cirrhosis with portal hypertension, jaundice, ascites • Peptic ulcer disease • Cancer - excluding basal cell carcinoma • Metastatic cancer - if so, do not check cancer 	
Required entry. Allow multiple options.
 
Note to data collector: Age and comorbidities will be used to calculate the age adjusted Charlson comorbidity index. Each of these is defined in the guide provided

	
 • Rheumatic or connective tissue disease • HIV/AIDS • Skin ulcers/cellulitis • Depression • Dementia • On Warfarin 	
Simpson grade	Dropdown list/check box 
 • 1-GTR • 2-GTR • 3-GTR • 4-STR • 5-STR 	Required entry. Allow one option only

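### Baseline WHO performance status is compulsory with no not-documented code, so a guessed value cannot be told from a recorded one in the PS-stratified analyses

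*Protocol*

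**What the plan says.** Section 3.8.1 lists the baseline clinical variables, including "the World Health Organisation (WHO) performance status (PS) and the age adjusted Charlson comorbidity index (ACCI". In Appendix 1, on the baseline clinical page, the field "WHO Performance status" offers 0, 1, 2, 3 and 4 and carries the rule "Required entry. Allow one option only". There is no level for a PS that the notes do not support.

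Other fields on the form do have such a level. Ethnicity has NA. For brain invasion, section 3.8.3 asks for "presence of any reported brain invasion (yes / no / not reported" and the surgery page of Appendix 1 provides NA.

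Section 3.10.1 uses PS as a stratifier: "Patients will be split based on WHO PS into two categories: 0-1 and 2-4". The strata serve two competing-risk analyses, one of primary intervention and one of disease progression, and the curves are compared with the training data. Stage 4 in section 3.10.2 may then re-cut the PS and ACCI strata.

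Section 3.8.3 also asks for "Simpson grade (as recorded by the surgeon in the operative notes". In Appendix 1 the field "Simpson grade" is a compulsory single choice from "1-GTR • 2-GTR • 3-GTR • 4-STR • 5-STR".

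**The concern.** The tumours were found in 2009-10 on scans done for other reasons (sections 3.1 and 3.2). Section 3.6 expects all items to be routinely available, but that is an expectation and not a rule for the case where it fails. Section 3.2 excludes patients whose notes or scans are unavailable, not patients whose notes lack a PS. Appendix 1 also lets a patient be entered as dead or lost to follow-up at the first management decision, so people with little clinic contact still need a PS. The local team enters baseline and outcome in one record, and no masking of the baseline entry is stated.

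If the notes give no basis for a grade, the collector has to pick one, possibly knowing how the patient fared. Once stored as 0 to 4, that value looks like any recorded one. No later analysis plan could count, impute or exclude it. At stake is the PS 0-1 v 2-4 contrast in the two cumulative-incidence analyses. Stage 4 is also exposed, because it adjusts the strata in search of significant differences and could pick up a contrast that the coding created.

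**Working it through.** **The plan's own figures.** Section 3.4 needs 100 events at a 10% progression risk: 100 / 0.10 = 1000 patients, as stated, raised to at least 1500. At 10%, 1500 patients give 150 events. The form issue changes none of this. The 10% is used below.

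**Assumptions not in the documents.** Share truly PS 2-4, q = 20%. PS undocumented in u = 10%, 20% or 40%, unrelated to true PS or outcome. Progression is treated as a simple yes/no risk r = 10%, without censoring or competing events.

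**A. True risk equal in both strata (ratio 1).**

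*Outcome-blind coding.* Guessing 2-4 at rate q, or defaulting everyone to 0-1, mixes groups with the same risk. The result is 10.0% v 10.0%, so no false contrast.

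*Outcome-informed coding.* Suppose undocumented patients with an event are never guessed as 2-4, and those without are guessed 2-4 at rate q. Then:

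- Risk in recorded PS 2-4 = (1 − u)qr / [q(1 − ur)] = (1 − u)r / (1 − ur)
- Risk in recorded PS 0-1 = [r − (1 − u)qr] / [1 − q(1 − ur)]

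| u | PS 2-4 | PS 0-1 | Ratio |
|---|---|---|---|
| 10% | 0.09 / 0.99 = 9.1% | 0.082 / 0.802 = 10.2% | 0.89 |
| 20% | 0.08 / 0.98 = 8.2% | 0.084 / 0.804 = 10.4% | 0.78 |
| 40% | 0.06 / 0.96 = 6.3% | 0.088 / 0.808 = 10.9% | 0.57 |

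If patients with an event are instead guessed 2-4 at half the rate q, the ratios are 0.94, 0.89 and 0.78. With q = 10% and the stronger rule they are 0.90, 0.80 and 0.60.

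In patients, at u = 20% and N = 1500: the true PS 2-4 stratum has 1500 × 0.20 = 300 patients and 30 events. The recorded one has 1500 × 0.196 = 294 patients and 1500 × 0.016 = 24 events.

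**B. A true difference exists: 11.25% (PS 0-1) v 5.0% (PS 2-4), ratio 0.44, u = 20%.**

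- Outcome-blind random guessing: PS 2-4 = (0.008 + 0.004) / 0.20 = 6.0%; PS 0-1 = 0.088 / 0.80 = 11.0%; ratio 0.55 (diluted).
- Default to 0-1: PS 2-4 = 5.0%; PS 0-1 = 0.092 / 0.84 = 11.0%; ratio 0.46 (nearly unchanged).
- Outcome-informed as in A: PS 2-4 = 0.008 / 0.196 = 4.1%; PS 0-1 = 0.092 / 0.804 = 11.4%; ratio 0.36 (exaggerated).

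**C. Intervention, the other planned analysis.** Further assumptions: 25% PS 2-4, 20% undocumented, true intervention risk 12% and mortality 40% in both strata. A quarter to a half of the undocumented dead are coded 2-4, none of them having had an intervention, and everyone else undocumented is coded 0-1.

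- PS 2-4: 0.024 / 0.22 = 10.9% to 0.024 / 0.24 = 10.0%
- PS 0-1: 0.096 / 0.78 = 12.3% to 0.096 / 0.76 = 12.6%

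**The case against.** The strongest reply is that Table 1 defines PS by function (work, self-care, time in bed or chair), so grading it from narrative notes is ordinary abstraction. Section 3.9 promises data collection guides that are not shown and may contain a rule. Section 3.7 plans two test phases before go-live, and Appendix 1 is a guide for developers that does not say a compulsory field blocks saving. Sites keep a link file, so a doubtful entry could be checked against source. All of this stands, and it limits the problem to charts that give no basis for a grade. It does not remove it: the form as specified offers no way to mark those charts, so nobody would know which entries to check. The NA on the T2/FLAIR items is also a weak comparison, since it is there for CT-only imaging. Ethnicity and brain invasion are the relevant ones.

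A reader might infer more than the documents support:

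- *That PS must be invented, or is often absent.* The documents give no undocumented share, and narrative notes may suffice.
- *That the PS results are biased.* Under the assumptions above, outcome-blind coding gives no false contrast and at most dilutes a real one. A false contrast needs coding informed by outcome, which the protocol permits but does not show.
- *That PS-specific mortality is distorted.* Mortality is not a planned PS-stratified outcome; in these analyses it acts as a competing event.
- *That Simpson grade is part of the same bias.* It enters no PS analysis and comes from the operative note at the time of surgery, not from the diagnostic chart. Section 3.8.3 and the form do not contradict each other; they leave the unrecorded grade uncovered.
- *That the main validation is compromised.* Section 1.1 bases the risk groups on MRI parameters, so calibration, the Brier score and the discrimination measures do not use PS directly.

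**Conclusion.** The point holds as a limited weakness of the data form. A baseline PS that the notes do not support can only be entered as a guess that looks like data. The exposure is confined to the PS-stratified intervention and progression analyses, their comparison with the training data, and Stage 4.

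The size cannot be known from the documents. It ranges from nothing (outcome-blind coding, no true difference) to an apparent progression ratio of 0.89 to 0.57 when the truth is 1 (q = 20%, u = 10-40%, patients with an event never guessed as 2-4). These are illustrations of a possible range, not predictions. They depend on the assumed coding behaviour and on missing PS being unrelated to true PS and outcome. The opposite coding habit would push the ratio above 1.

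The missing Simpson level is separate and minor, and touches only the descriptive surgical results.

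**What to change.** In Appendix 1, add *Not documented* to the baseline WHO PS field. In the data collection guide, tell collectors to grade PS only from entries made at or before diagnosis and not to infer it from the later course. If the team wants to accept the first clinic letter after the scan, that window should be written down. In section 3.10.1, commit to reporting the share not documented and to repeating the PS-stratified analyses in patients with recorded PS. Imputation can be left as an option for the analysis plan.

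Separately, add *Not recorded* to the Simpson grade field, so that the form matches the instruction to take it only from the surgeon's note.

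The cost is two extra list options, a line in the guide and one repeat analysis. The downside is some visible missing PS and slightly wider intervals. The form is the place to act, because an analysis plan cannot recover information that was never captured.
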